9. SAFETY

9.1 Safety Variables

- Vital signs

- Physical examination
- Clinical laboratory tests
- Adverse events

9.2 Laboratory Evaluations

At screening, the HIV-1 and HIV-2 tests, CMV, hepatitis screen, and β -HCG serum pregnancy tests (only for women of child-bearing potential) will be performed. Laboratory safety tests will consist of the following:

Serum chemistry: sodium, potassium, chloride, bicarbonate, BUN, creatinine, glucose, calcium, AST/SGOT, ALT/SGPT, total bilirubin (fractionate if total >1.5 times normal), alkaline phosphatase, albumin, GFR, total protein, HbA1C

Hematology (CBC): hemoglobin, hematocrit, platelets, WBC, WBC differential

The Investigator will review all clinically relevant laboratory results requested in the protocol. The diagnosis associated with any clinically significant laboratory deviations should be recorded as an AE and should indicate the underlying abnormality or diagnosis (such as renal insufficiency) as opposed to the observed deviation in laboratory results (such as elevated creatinine). If there is no underlying abnormality linked to a clinically significant abnormal laboratory value, the observed deviation should be reported as the AE.

9.2.1 Pulse Oximetry

Pulse oximetry will be used to observe oxygen saturation when measuring vital signs at the infusion visit (Reference Appendix 1). Pulse oximetry will be monitored throughout infusion and continuously for 2 hours post-infusion. Subjects should have a resting oxygen saturation of $\geq 93\%$ prior to infusion. Subjects requiring oxygen, need the peripheral artery oxygen saturation (SaO_2) to be $\geq 93\%$ when given a maximum of 2L/minute supplemental O_2 via nasal cannula. Infusion toxicity will be assessed based on decreases in oxygen saturation during infusion. The infusion will be stopped if the oxygen saturation does not return to $>93\%$ within 3 minutes of initiating supplemental oxygen or if the subject requires greater than 2L/min supplemental oxygen to achieve the required saturation of $>93\%$. If this occurs, then subjects will be admitted to the hospital for observation.

9.2.2 Pregnancy

There is no information regarding allogeneic MSCs and its effects or potential risks to a fetus or unborn child. The Principal Investigator and DSMB must be notified within twenty-four hours of investigator's awareness of the pregnancy via facsimile if a study subject becomes pregnant during the study. Any two of the enumerated contraceptive items will be acceptable for meeting the studies contraceptive requirements as listed in paragraph 2 of section 8.2.2. Females will be defined as non-childbearing potential if surgically sterilized (i.e. bilateral tubal ligation, bilateral oophorectomy, or complete hysterectomy) or post-menopausal (defined as 12 months no menses with an alternative medical cause and with a follicle stimulating hormone $\text{FSH} \geq 25.8 \text{ IU/L}$). Non-sterilized males who are

sexually active with a female partner of childbearing potential must use any two of the acceptable forms of contraceptive items as listed below:

Acceptable forms of contraception include: 1) abstinence, 2) condoms (male or female) with a spermicidal agent, 3) diaphragm or cervical cap with spermicidal agent, 4) intrauterine device (IUD), 5) oral contraceptive, 6) injectable or transdermal hormonal contraceptive, 7) successful vasectomy with resulting azoospermia or azoospermia for any other reason, and 8) hysterectomy, bilateral oophorectomy, or tubal ligation.

Prior to study enrollment, women of childbearing potential must be advised of the importance of avoiding pregnancy during trial participation and the potential risk factors for a pregnancy. The subject must sign an informed consent and written authorization for use and disclosure of PHI document stating that the above-mentioned risk factors and the consequences were discussed with her.

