| Exclusion Criteria | 
 1. Be younger than 18 years of age. 2. Have a baseline glomerular filtration rate (GFR) < 30 ml/min 1.73m^2 estimated using the MDRD formula. 3. Indication for surgical revascularization or valve therapy. 4. Have known hypersensitivity or contraindication to aspirin; both heparin and bivalirudin; all available P2Y₁₂ inhibitors (clopidogrel, prasugrel, and ticagrelor); or any zotarolimus, cobalt, chromium, nickel, tungsten, acrylic, or fluoro polymers; or hypersensitivity to contrast media that cannot be adequately premedicated. 5. Have a hematologic abnormality as evidenced by hematocrit $< 25\%$, white blood cell $< 2,500/\text{uL}$ or platelet values $< 100,000/\text{uL}$ without another explanation. |

| | |
|--|---|
| | 
6. Have liver dysfunction, as evidenced by enzymes (AST and ALT) greater than three times the upper limit of normal.7. Have a bleeding diathesis or coagulopathy (INR > 1.3), cannot be withdrawn from anticoagulation therapy, or will refuse blood transfusions.8. Be an organ transplant recipient or have a history of organ or cell transplant rejection.9. Have a clinical history of malignancy within the past 2 years (i.e., subjects with prior malignancy must be disease free for 2 years), except curatively treated basal cell or squamous cell carcinoma, or cervical carcinoma.10. Have a condition that limits lifespan to < 1 year.11. Have a history of drug or alcohol abuse within the past 24 months.12. Be serum positive for HIV, hepatitis B sAg, or viremic hepatitis C.13. Be currently participating (or participated within the previous 3 months) in an investigational therapeutic or device trial.14. Be pregnant, nursing, or of childbearing potential and not on contraception. (May participate if on 2 forms of acceptable contraceptives).15. Any other condition that in the judgment of the Investigator would be a contraindication to enrollment or follow-up. |
|--|---|

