4.2. Exclusion Criteria

In order to participate in this study, a subject MUST NOT:

1. Be younger than 18 years of age.
2. Have a baseline glomerular filtration rate (GFR) < 30 ml/min 1.73m^2 estimated using the MDRD formula.
3. Indication for surgical revascularization or valve therapy.
4. Have known hypersensitivity or contraindication to aspirin; both heparin and bivalirudin; all available P2Y₁₂ inhibitors (clopidogrel, prasugrel, and ticagrelor); or

- any zotarolimus, cobalt, chromium, nickel, tungsten, acrylic, or fluoropolymers; or hypersensitivity to contrast media that cannot be adequately premedicated.
5. Have a hematologic abnormality as evidenced by hematocrit < 25%, white blood cell < 2,500/uL or platelet values < 100,000/uL without another explanation (per investigator discretion).
 6. Have liver dysfunction, as evidenced by enzymes (AST and ALT) greater than three times the upper limit of normal.
 7. Have a bleeding diathesis or coagulopathy (INR > 1.3), cannot be withdrawn from anticoagulation therapy, or will refuse blood transfusions.
 8. Be an organ transplant recipient or have a history of organ or cell transplant rejection.
 9. Have a clinical history of malignancy within the past 2 years (i.e., subjects with prior malignancy must be disease free for 2 years), except curatively treated basal cell or squamous cell carcinoma, or cervical carcinoma.
 10. Have a condition that limits lifespan to < 1 year.
 11. Have a history of drug or alcohol abuse within the past 24 months.
 12. Be serum positive for HIV, hepatitis B sAg, or viremic hepatitis C.
 13. Be currently participating (or participated within the previous 30 days) in an investigational therapeutic or device trial.
 14. Be pregnant, nursing, or of childbearing potential and not on contraceptive medications. (May participate if on 2 forms of contraceptives).
 15. Any other condition that in the judgment of the Investigator would be a contraindication to enrollment or follow-up.

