7 STUDY PROCEDURES

Time and Events Schedule

The Time and Events Schedule for the conduct of this study is shown in Table 1

Schedule of Assessments

| Table 1: Time and Events Table VISIT | | Screening | Baseline | Day 0 Infusion | Week 2 Post-Infusion | Month 1 Post-Infusion | Month 3 Post-Infusion | Month 6 Post-Infusion | Month 12 Post-Infusion |
|--|---------------------------------|--------------------------------|---------------------|---------------------|----------------------|-----------------------|-----------------------|-----------------------|------------------------|
| | | Within 7 days Pre or Post-Cath | 0-30 days post-Cath | 0-30 days post-Cath | ± 5 days | ± 2 weeks | ± 2 weeks | ± 2 weeks | ± 2 weeks |
| Informed Consent ¹ | | X | | | | | | | |
| Medical History | | X | | | | | | | |
| Physical Exam & Vital Signs ² | | X | | X | X | X | X | X | X |
| 12-lead Electrocardiogram (ECG) | | X | | X | | X | X | X | X |
| Concomitant Medications ³ | | X | X | X | X | X | X | X | X |
| Randomization ⁴ | | | X | | | | | | |
| IV Infusion Treatment ⁵ | | | | X | | | | | |
| Coronary Angiogram ⁶ | | X | | | | | | X | |
| FFR, CFR, IFR, IVUS, and/or OCT (optional) ⁷ | | X | | | | | | X | |
| Brachial Artery Ultrasound ⁸ | | | X | | X | X | X | X | |
| Bone Marrow Biopsy ⁹ | | | | | | | X | | |
| Questionnaires ¹⁰ | | | X | | X | X | X | X | |
| Review Adverse Events | | | X | X | X | X | X | X | X |
| Laboratory Testing ¹¹ | Hematology & Chemistry | X | | X | | X | X | X | |
| | Coagulation | X | | | | | X | X | |
| | Urinalysis | X | | | | | X | X | |
| | HbA1c | X | | | | | X | X | |
| | Biomarkers (SST) (includes PRA) | | X | | X | X | X | X | |
| | Immune Monitoring (MNC) | | X | | X | X | X | X | |
| | Genetic Testing (DNA and RNA) | | | X | | | | X | |
| | EPC-CFU assay | | X | | X | X | X | X | |
| | Viral Serology | X | | | | | | | |
| | Serum Pregnancy Test | X | | X | | | | | |

Time and Events Table Key:

1. Informed consent can be obtained Pre- or Post- cardiac catheterization. The first angiogram is clinically indicated.

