complete the IIEF questionnaire, and only female subjects will be asked to complete the SQOL-F questionnaire.

11. Subjects must be fasting for at least 8 hours prior to blood collection as required by standard of care. If labs were performed as “Standard of Care” within 7 days of signing ICF, those results may be extracted from patient medical records and used for the screening visit in this study. The minimal laboratory requirements include:

Hematology Tests:

Complete Blood Count with Differential (WBC, RBC, hemoglobin, hematocrit, MCV, and platelets; Diff: neutrophils, lymphocytes, monocytes, eosinophils, and basophils).

Chemistry Tests: (fasting required)

Comprehensive Metabolic Panel (glucose, sodium, potassium, chloride, bicarbonate, blood urea nitrogen, creatinine, total protein, albumin, alkaline phosphatase, total bilirubin [fractionate if total >1.5 times normal], alanine transaminase (ALT), aspartate transaminase (AST), and GFR).

Coagulation Tests: Prothrombin time (PT/INR), activated partial thromboplastin time (aPTT).

Urinalysis: Routine Urinalysis with reflex to culture.

Glycosylated Hemoglobin: HbA1c

Biomarkers: SST: (2 Gold or Tiger top serum separator tubes) Transcriptomic/proteome (RNA, mRNA, protein samples, and telomerase, akt); growth factors (sdf-1, notch); functional assays (cell-growth rate, VEGF, and CFU assays), PRA, and more.

Immune monitoring: MNCs: (2 Green top sodium heparin tubes) CD3*CD25* or CD3*CD69* and more.

Gene Expression: peripheral blood will be collected prior to infusion on Day 0, and at the 6 month follow up visit to analyze DNA & RNA (DNA to be collected at one time point only).

EPC-CFU Assay: Blood samples (5 Lavender top tubes) to measure Endothelial Progenitor Cell-Colony Forming Units (EPC-CFU).

Viral Serology: Infectious disease tests – HIV, HIV 2, Hep B (HBsAg), Hep C (Anti-HCV), and CMV.

Serum Pregnancy Test: Serum β HCG test will be completed at screening and within 36 hours prior to infusion in women of childbearing potential only.

If subjects are unable to come to the site for specified visits alternative methods for assessments (e.g., phone contact, virtual visit, alternative location for assessments, including local labs or imaging centers) could be implemented when necessary.

8 Study Phases and Visits

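### Section 9.2.2 defines post-menopausal with the wrong word (*with* for *without* another medical cause), reversing childbearing class for non-sterilised women with 12 months' amenorrhoea and a documented FSH of at least 25.8 IU/L

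*Combined protocol and SAP*

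**What the plan says.** Section 9.2.2 (Pregnancy) gives two routes to being classed as not of childbearing potential. One is surgical sterilisation. The other is being post-menopausal, which requires "12 months no menses with an alternative medical cause" together with an FSH of at least 25.8 IU/L. The parts of the second route are joined by *and*. Nothing else in the protocol defines post-menopausal or corrects this wording.

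The class is used in these places:

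- **Pregnancy testing.** Table 1 in section 7 schedules the serum test at Screening and Day 0 ("Serum Pregnancy Test | X | | X"). Item 11 of the table key asks for it at screening and "within 36 hours prior to infusion in women of childbearing potential only". Section 9.2 limits the screening test in the same way: "pregnancy tests (only for women of child-bearing potential) will be performed".
- **Eligibility.** Exclusion 14 in section 4.2 bars anyone who would "Be pregnant, nursing, or of childbearing potential and not on contraceptive medications". The synopsis version adds "May participate if on 2 forms of acceptable contraceptives".
- **Advice.** Section 9.2.2 says that before enrolment "women of childbearing potential must be advised of the importance of avoiding pregnancy during trial participation".

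The same section opens with the reason for caution: "There is no information regarding allogeneic MSCs and its effects or potential risks to a fetus or unborn child".

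**The concern.** Amenorrhoea that another medical condition explains is not menopause. A definition that demands such a cause contradicts the term it defines, and one that rules it out would make sense. The slip matters because this is an operative rule: it decides who is tested for pregnancy, who must use contraception and who is counselled.

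The error runs in two directions. In one, a naturally menopausal woman is treated as fertile, has two pregnancy tests she does not need, and must use two contraceptive methods or be excluded. In the other, a woman whose periods stopped for another medical reason is treated as unable to conceive and passes through screening and infusion without a scheduled pregnancy test. The second direction is the safety question, given that the protocol reports no knowledge of fetal risk.

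**Working it through.** There is no stated figure to reproduce. The check is one of logic.

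**Inputs, all from section 9.2.2.** Let S = surgically sterilised, A = 12 months without menses, C = another medical cause for the amenorrhoea, F = FSH of at least 25.8 IU/L documented.

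**Rules for not of childbearing potential.**

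- As written: S or (A and C and F)
- With *without*: S or (A and not C and F)

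**Comparison.** Four yes/no conditions give 2 × 2 × 2 × 2 = 16 combinations.

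- S = yes (8 combinations): both rules give not of childbearing potential. No change.
- S = no, A = no (4 combinations): both give childbearing potential. No change.
- S = no, A = yes, F = no (2 combinations): both give childbearing potential. No change.
- S = no, A = yes, F = yes (2 combinations): both change.

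So 2 of 16 combinations differ. For a non-sterilised woman with 12 months' amenorrhoea, separating a low FSH from a missing one:

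| FSH | Other medical cause? | As written | Corrected |
|---|---|---|---|
| ≥ 25.8 IU/L | no (natural menopause) | childbearing | not childbearing |
| ≥ 25.8 IU/L | yes | not childbearing | childbearing |
| < 25.8 IU/L | no | childbearing | childbearing |
| < 25.8 IU/L | yes | childbearing | childbearing |
| missing | no | childbearing | childbearing |
| missing | yes | childbearing | childbearing |

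The class changes in 2 of 2 rows with a qualifying FSH and in 0 of 4 rows otherwise. These are counts of cases in the rule, not frequencies of patients.

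**Where an FSH value would come from.** FSH appears neither in Table 1, nor in the minimum laboratory list in item 11 of its key, nor in the safety laboratory list in section 9.2. Scheduled testing alone therefore never produces the qualifying value. The reversal arises only if a result is available from elsewhere, such as the medical record.

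**What the unsafe row switches off.** A woman in the second row would not have the screening test or the pre-infusion test (2 of the 2 scheduled), would not be subject to the contraception part of exclusion 14, and would not fall under the advice requirement.

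**What stays in force for her.** The pregnant and nursing parts of exclusion 14 do not depend on the class. Nor does notification within 24 hours of a pregnancy becoming known (section 9.2.2), withdrawal on pregnancy (section 9.9), or the investigator's discretion under exclusion 15. The gap is in detecting and preventing pregnancy; the rules for acting on a known pregnancy still cover her.

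**The case against.** The strongest reply is that the slip is self-evident. The term being defined is post-menopausal, any clinician knows that another cause for amenorrhoea argues against menopause, and most investigators will read *without*. The unsafe case also needs several things at once: 12 months' amenorrhoea from another cause, an off-schedule FSH at or above the threshold, remaining fertility, and an investigator who applies the text literally. All of this stands as a limit on how often the error could bite. It does not make the rule right, since an investigator has to depart from the written text to apply the intended one.

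Four stronger readings are tempting, and the documents do not support them.

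- **That any woman with a qualifying FSH is misclassified.** In a sterilised or still menstruating woman both wordings give the same class.
- **That the misclassified woman loses every pregnancy safeguard.** The pregnant and nursing exclusions, notification and withdrawal apply whatever her class.
- **That the lack of pregnancy tests at the five post-infusion visits is part of this error.** That schedule applies to every woman, does not result from the wording, and is untouched by the correction.
- **That a known number of participants is affected.** The documents give no expected number of women in this trial, nor their menopausal status or FSH.

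**Conclusion.** The definition is wrong as written, on a safety and eligibility point. The reversal is confined to non-sterilised women with 12 months' amenorrhoea and a documented FSH of at least 25.8 IU/L, where both possible classes are inverted. With FSH below the threshold or missing, the rule errs on the cautious side under either wording.

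This rests on two assumptions. The first is that *without* is intended, which follows from the meaning of the term. The second is that the conditions are cumulative, as the joining *and* indicates. How many of the 30 planned participants could be affected cannot be estimated. Sample size, endpoints and statistical analysis are not touched. The severity is minor.

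**What to change.** In section 9.2.2, replace *with* by *without* before the reference to an alternative medical cause, and leave the rest of the definition, including the FSH threshold, unchanged. This can go into the next amendment, under the IRB approval that section 12.2 requires for amended text. It adds no test, visit or blood draw.

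The correction has one limit. Because FSH is not scheduled, a naturally menopausal woman with no FSH result will still count as of childbearing potential afterwards, so she will still be tested and asked to use two methods. That errs on the cautious side and needs no further change for this point.

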9.2.3 Determination of Infusion Toxicity

Infusion toxicity will be evaluated by continuously monitoring the subject's vital signs and O₂ saturation by pulse oximetry from the time of allogeneic hMSCs administration until two hours after infusion is complete. Since there is no specific or antidotal therapy for AEs arising from allogeneic hMSCs, any toxicity that may arise during a subject's participation in this study should be managed with supportive measures at the discretion of the treating physician.

9.2.4 Subject Stopping Guidelines

This guideline is to be used to indicate boundaries requiring discussion by the Data and Safety Monitoring Board (DSMB) and is designed to assist the independent DSMB in overseeing the study. The DSMB may also request additional interim analyses and develop other criteria including provision for monitoring of potential late effects to determine when to intervene in the enrollment or treatment of subjects in the study.

The first more conservative stopping guideline is to monitor subjects for unexpected SAEs where there is a reasonable possibility that the study product or administration procedure caused the event within 30 days of administration including cardiorespiratory distress during infusion, subject death, myocardial infarction, hemodynamically unstable ventricular tachycardia, stroke, or more than two related, \geq Grade 3 AEs (based on the NIH CTCAEv5). Study accrual and further treatment of subjects will be put on hold (temporary suspension of study drug administration, pending a safety investigation) if any subjects experience one of these events. The DSMB will be notified within 24 hours of the occurrence of these events and will be convened within 3 business days to review the event and study.

The following are subject stopping guidelines:

- Any subject who develops persistent (that is, still existing more than 3 hours after the end of IP infusion) cardiorespiratory signs or symptoms (for example, shortness of breath, tachypnea, tachycardia, hypotension, or palpitations) will continue with all scheduled follow-up if such follow-up is considered safe in the opinion of the Investigator.
- Any subject whose infusion is stopped due to cardiorespiratory distress will receive no further IP infusions but will continue with all scheduled follow-up if such follow-up is considered safe in the opinion of the Investigator.
- Any subject who develops any sign or symptom that, at the discretion of the Investigator, warrants the discontinuation of infusion will receive no further IP infusions but will continue with all scheduled follow-up if such follow-up is considered safe in the opinion of the Investigator.
- Infusion of the IP may be stopped if there is an adverse event that the Investigator believes is related to the IP or if there is an issue with the IP infusion.
- The proportion of subjects experiencing TE-SAE as defined in Section 2.2.1 will be monitored within 30 days of injection. This guideline is designed to assist the independent DSMB in overseeing the study and indicate boundaries needing discussion by the DSMB. The DSMB may also request additional interim analyses and develop other criteria including provision for monitoring of potential late effects to determine when to intervene in the enrollment or treatment of subjects in the study.
- The stopping guidelines serve as a mechanism for consultation with the DSMB for additional review and are not formal “stopping rules” that would mandate automatic closure of study enrollment. It is designed to assist the independent DSMB in overseeing the study. The DSMB may also request additional interim analyses and develop other criteria including provision for monitoring of potential late effects to determine when to intervene in the enrollment or treatment of subjects in the study.

